5.5. Exploratory Efficacy Variables

5.5.1. Definition

5.5.1.1. Amyloid Disclosure Assessments

Concerns about Alzheimer's Disease Dementia

The Concerns about Alzheimer's Disease Dementia scale is administered during screening prior to and after amyloid disclosure and after randomization at Months 1, 3, 9, 21, 42, and 54 (or early termination). The scale is a short self-report instrument that assesses an individual's concern about developing Alzheimer's disease dementia. The questionnaire asks subjects to rate

their agreement with 6 statements related to concerns about AD dementia with ratings that range from 1 (strongly disagree) to 5 (strongly agree).

Change from baseline at each time point will be calculated for each statement score. For off-treatment visits, change from the off-treatment baseline (see Section 2.4) will also be calculated.

Future Time Perspective (FTP) Scale

The FTP scale⁵ is administered during screening prior to and after amyloid disclosure and after randomization at Months 1, 3, 9, 21, 42, and 54 (or early termination). The FTP scale asks subjects to rate their agreement with 10 statements related to perception of time with ratings that range from 1 (very untrue) to 7 (very true). For the first 7 statements, higher scores indicate a positive future time perspective (e.g., “My future is filled with possibilities”). For the last 3 statements, higher scores indicate a negative time perspective (e.g., “There are only limited possibilities in my future”). An overall FTP score is the average of the 10 individual statement scores, after reverse-scoring the last 3 statement scores. A higher overall FTP score indicates a more positive future time perspective.

Change from baseline at each time point will be calculated for each statement score and for the overall FTP score. For off-treatment visits, change from the off-treatment baseline (see Section 2.4) will also be calculated.

5.5.1.2. Computerized Cognitive Battery

The CogState Brief Battery⁶ will be administered during screening prior to amyloid testing and 5 to 10 days before randomization, and every 6 months after randomization through Month 54 (or early termination). The CogState Brief Battery includes tasks that use playing cards as stimuli: detection, identification, one card learning, and one back. For each, the test software measures the speed and accuracy of the subject’s responses.

- The **detection** task is a measure of information processing speed and uses a well-validated simple reaction time paradigm. In this task, the playing cards are all jokers. The subject is asked to press the “yes” key as soon as the card in the center of the screen turns face up. The reaction time is measured in milliseconds and \log_{10} -transformed. The overall score is the average of all log-transformed reaction times. A lower score is better.
- The **identification** task is a measure of visual attention and uses a well-validated choice reaction time paradigm. In this task, the playing cards are all either red or black jokers. The subject is asked whether the card currently being presented in the center of the screen is red. The subject responds by pressing the “yes” key when the joker card is red and “no” when it is black. The reaction time is measured in milliseconds and \log_{10} -transformed. The overall score is the average of all log-transformed reaction times of correct responses. A lower score is better.
- The **one card learning** task is a measure of visual recognition memory and uses a well-validated pattern separation paradigm. In this task, the subject is asked whether the playing card presented in the center of the screen was seen previously in this task. The subject responds by pressing the “yes” or “no” key. Because no card has been presented yet, the first

response is always “no”. The overall score is the arcsine transformation of the square root of the proportion of correct responses. A higher score is better.

- The **one back** task is a measure of working memory and uses a well-validated n-back paradigm. In this task, the subject is asked whether the playing card being presented is the same as the one presented immediately previously. The subject responds by pressing the “yes” or “no” key. Because no card has been presented yet, the first response is always “no”. The reaction time is measured in milliseconds and \log_{10} -transformed. The overall score is the average of all log-transformed reaction times of correct responses. A lower score is better.

In addition to the CogState Brief Battery above, computerized testing also includes the Face Name Associative Memory Exam¹⁴:

- The **Face Name Associative Memory Exam** begins with an exposure in which the subject is shown 16 faces, one at a time, for 2 seconds in a random order. For each face the subject is asked to decide whether “the name goes with that face”. Once this is completed, each of the 16 faces is presented again. For each face the subject must recall the name that was associated with that face on the initial trial and indicate this by typing the name into the computer. The correct number of face-name pairs is recorded as an initial learning score. After a delay the subject is shown each face in turn with 3 names given beneath that face. The subject must select the name that was initially paired with the face. The number of correct responses is recorded (range: 0 to 16; higher score is better).

Change from baseline at each time point will be calculated for each score. For off-treatment visits, change from the off-treatment baseline (see Section 2.4) may also be calculated.

5.5.1.3. Cognitive Function Index-acute (CFI-a)

The CFI-a is a modified version of the CFI, a subject and informant-reported outcome measure developed by Janssen. The subject-reported and informant-reported CFI-a’s are assessed on the same schedule: 5 to 10 days before randomization, then every 3 months through Month 54 (or early termination if not performed at the previous visit). This assessment includes 14 questions similar to those in the CFI (see Section 5.4.1.5) that evaluate the subject’s perceived ability to perform high-level functional tasks in daily-life and sense of overall cognitive functional ability. Study subjects and their informants independently rate the subject’s abilities based on their current or most recent experience. The scale uses frequency (never = 0, rarely = 1, sometimes = 2, often = 3, or always = 4) to measure impairment, with “always” indicating greatest impairment. Responses of “I do not drive”, “Does not apply”, or “I do not work or volunteer” will be scored as 0.

The CFI-a total score is the sum of the 14 questions, with higher scores indicating greater impairment (range = 0 to 56). If there are fewer than 5 (<30%) missing items, an imputed total score will be calculated as a prorated total based on the observed items:

$$14 * \left(\frac{\text{Total score of non-missing items}}{\text{Total number of non-missing items}} \right)$$

Imputed total scores will be rounded to 1 decimal place. If there are 5 or more missing items, the total score will be missing. A subject-reported and an informant-reported total score will be calculated. Change from baseline in the CFI-a total score will be calculated at each time point. For off-treatment visits, change from the off-treatment baseline (see Section 2.4) will also be calculated.

5.5.1.4. Financial Capacity Instrument – Short Form (FCI-SF)

The FCI-SF is administered at selected centers during screening 5 to 10 days before randomization, annually after randomization through Month 48, and at Month 54 (or early termination, if not collected at the subject's previous visit). The FCI-SF is a 37-item psychometric instrument that measures financial capacity. Items are summed to form 5 component performance scores:

- Mental calculation (2 items, range: 0-4),
- Financial conceptual knowledge (4 items, range: 0-8),
- Single checkbook/register (10 items, range: 0-20),
- Complex checkbook/register (14 items, range: 0-28),
- Bank statement management (7 items, range: 0-14)

Correct responses are scored as 2 and incorrect responses are scored as 0 (a partial credit score of 1 is possible for some items). Each item in the mental calculation, financial conceptual knowledge, and bank statement management tasks has a time limit for providing a response. For the checkbook tasks, there is a time limit to complete all items within the task. If a response was given after the time limit, the item was scored as 0 (even if the response was correct).

An FCI-SF total score is calculated as the sum of all 37 items. A component score and the Total Score are missing if any item in the component score is missing.

The time, in seconds, to complete the items listed below is recorded. If the completion time exceeded the time limit for the item(s), the maximum allowed time was recorded.

- Medical deduction problem (maximum time: 90 seconds)
- Income tax problem (maximum time: 90 seconds)
- Single checkbook/register (maximum time to complete all items: 240 seconds)
- Complex checkbook/register (maximum time to complete all items: 300 seconds)

A checkbook/register composite time will be calculated as the sum of the single and complex checkbook/register times and a total composite time will be calculated as the sum of all 4 individual component times.

Change from baseline at each time point will be calculated for each performance and timing parameter. For off-treatment visits, change from the off-treatment baseline (see Section 2.4) may also be calculated.

5.5.1.5. Amsterdam IADL Questionnaire (A-IADL-Q)

The A-IADL-Q will be administered at selected centers only during screening, annually after randomization through Month 48, and at Month 54 (or early termination, if not collected at the subject's previous visit). The A-IADL-Q is a computerized questionnaire aimed at measuring difficulties with complex daily activities. It is completed by the informant of the subject. The A-IADL-Q consists of 70 items and for each item difficulty is rated on a 5-point scale. To optimize individual differences in premorbid IADL activities, items are tailored to individual responses. If the patient had not performed the main activity, more detailed items on that activity are skipped.

The total score is calculated using an item response theory method of scoring. Item response theory assumes that ordered-categorical item responses represent an underlying construct. In this case, the construct is IADL functioning, ranging from disability to ability. The total score is normally distributed (mean = 50, standard deviation = 10), with higher scores indicating better functioning⁴.

Change from baseline at each time point will be calculated for the IADL total score. For off-treatment visits, change from the off-treatment baseline (see Section 2.4) may also be calculated.

5.5.2. Analysis Methods

All exploratory efficacy endpoints will be summarized with descriptive statistics. Inferential analyses may be performed to evaluate the treatment effect. The endpoints may also be summarized for the off-treatment period. Association between the endpoints and the cognitive endpoints will be explored.

6. SAFETY

All safety summaries will be presented for the on-treatment period and the off-treatment period,

6.1 Adverse Events

The verbatim terms used in the CRF by investigators to identify adverse events will be coded using the Medical Dictionary for Regulatory Activities (MedDRA). Any AE occurring on or after the date of the initial administration of study medication through the day of last dose plus 7 days is considered to be treatment emergent. If the event date is recorded as partial or completely missing, then the event will be considered to be treatment emergent unless it is known to be prior to the first administration of study medication based on a partial onset date or resolution date. All reported treatment-emergent adverse events will be included in the analysis. For each adverse event, the number and percentage of subjects who experience at least 1 occurrence of the given event will be summarized by treatment group. AEs in the off-treatment period are the AEs with onset more than 7 days after the last dosing.

Summary tables will be provided for:

- AEs
- AEs with a fatal outcome

- Serious AEs (SAEs)
- AEs leading to discontinuation of study medication (events with action taken of ‘drug withdrawn’)
- AEs leading to termination of study participation (events associated with a trial termination reason of ‘adverse event’)
- AEs by severity

AEs will also be summarized by age group, by gender, and by race. In addition to the summary tables, listings will be provided for subjects who:

- Died
- Had SAEs
- Had AEs leading to discontinuation of study medication or termination of study participation

The above listings will include events with onset during the screening phase.

Incidence of other treatment-emergent adverse events of special interest will be summarized. Hypopigmentation related and retinal related adverse events are identified by the investigator on the AE eCRF page and include:

- Hypopigmentation Related Adverse Events
 - Hair and skin hypopigmentation (events related to lighting hair, skin coloration, or iris coloration)
- Retinal Related Adverse Events
 - Retinal changes

Hepatic related treatment-emergent adverse events will also be summarized. Adverse events related to abnormal LFTs are defined as follows:

Events belonging to the MedDRA Drug Related Hepatic disorders SMQ – comprehensive search

In addition, other adverse event clinical MedDRA PT clusters will be summarized by treatment during the on-treatment phase and off-treatment phase of the study (including but not limited to rash related, sleep disorder related, depression related, anxiety related adverse events).

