### 9.1.2. Screening Phase

After providing written informed consent, subjects may be screened over a period of approximately 90 days to assess their eligibility for the study according to the inclusion and exclusion criteria defined for this study (see Section 4). If needed for biomarker collection, data interpretation, or logistical reasons, this period can be prolonged with written approval of the sponsor.

During screening, 4 primary screening steps will be assessed as shown in Figure 5. In addition, part of the baseline cognitive, functional, performance, and medical resource utilization/health outcomes measures will be performed during the screening period, as described further below. The complete list of assessments is noted in the Time and Events Schedule. Assessments for **Step III** (MRI) and **Step IV** (Elevated Amyloid Accumulation) may only be performed after the subject is determined to be still eligible for the study after review of results from **Step I** (General Health) and **Step II** (Clinical Scales). Step I and II can occur in any order, however, a subjects' history should be obtained before all other study activities. The history should include questions to ensure appropriateness to participate in the study (eg, availability of study partner, current symptomatic AD treatments, unstable medical illness, extended travel or upcoming surgeries, etc.). **Step III** must be completed before **Step IV**. The investigator must review the MRI results before the subject undergoes amyloid testing. The order of individual assessments within a step

is not fixed, unless otherwise indicated, and may differ by site depending on logistical aspects and subject preferences, provided the defined visit windows are maintained.

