## **Adverse Events**

The verbatim terms used in the eCRF by investigators to identify AEs will be coded using the Medical Dictionary for Regulatory Activities (MedDRA). All reported AEs with an onset during the double-blind treatment phase and AEs that have worsened in intensity since baseline (ie, treatment-emergent adverse events [TEAEs]) will be included in the analysis. For each TEAE, the percentage of subjects who experience at least 1 occurrence of the given event will be summarized by treatment group.

Summaries, listings, datasets, or subject narratives may be provided, as appropriate, for those subjects who die, who discontinue treatment due to an AE, or who experience a severe or serious AE.

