## 12.1. Definitions

### 12.1.1. Adverse Event Definitions and Classifications

#### Adverse Event

An AE is any untoward medical occurrence in a clinical study subject administered a medicinal (investigational or non-investigational) product. An AE does not necessarily have a causal relationship with the treatment. An AE can therefore be any unfavorable and unintended sign (including an abnormal finding), symptom, or disease temporally associated with the use of a medicinal (investigational or noninvestigational) product, whether or not related to that medicinal (investigational or noninvestigational) product. (Definition per International Council for Harmonisation [ICH]).

This includes any occurrence that is new in onset or aggravated in severity or frequency from the baseline condition, or abnormal results of diagnostic procedures, including laboratory test abnormalities.

Note: The sponsor collects AEs starting with the signing of the ICF (refer to Section 12.3.1).

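### The SAP's treatment-emergent rule omits the protocol's worsening part, so an adverse event that starts in screening and worsens on drug can be left out of the TEAE tables

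*SAP*

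**What the plan says.** **Protocol.** The Adverse Events part of section 11.10 defines treatment-emergent events in two parts. The first is onset in the double-blind phase. The second is "AEs that have worsened in intensity since baseline (ie, treatment-emergent adverse events [TEAEs]) will be included in the analysis".

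**SAP.** Section 6.1 (Adverse Events) has only a date window: "Any AE occurring on or after the date of the initial administration of study medication through the day of last dose plus 7 days". Three further rules in that section bear on how the window works:

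- An event with a partial or missing date counts as treatment-emergent "unless it is known to be prior to the first administration of study medication based on a partial onset date or resolution date".
- For the period after treatment, "AEs in the off-treatment period are the AEs with onset more than 7 days after the last dosing".
- "All reported treatment-emergent adverse events will be included in the analysis", so the treatment-emergent flag decides what the incidence tables contain.

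**Collection.** Protocol 12.1.1 notes that "The sponsor collects AEs starting with the signing of the ICF". Protocol 9.1.2 says that "subjects may be screened over a period of approximately 90 days to assess their eligibility".

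**The concern.** The two documents define the same term differently, and the SAP's version is narrower. An event that begins between consent and first dose and becomes more severe on drug is treatment-emergent under the protocol. Under the SAP it is not, if it keeps its pre-dose onset date.

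What is at stake is the descriptive safety summary. The SAP Introduction says that the study's objectives can no longer be evaluated after the early stop, so the safety tables are a main remaining output. A reader will expect them to follow the protocol's definition. The SAP's amendment history gives the cessation of the study as the reason for revision, which does not explain a narrower definition.

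**Working it through.** No arithmetic applies. The check sets the rules side by side.

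**1. Does the SAP window work by onset?** The verb in the main rule could be read either way. Two of the quoted sentences settle partial dates and off-treatment events by onset, with the resolution date as a second test for partial dates. A third sentence in SAP 6.1 says that the listings of deaths, SAEs and events leading to discontinuation or termination include events that began in screening. It would be unnecessary if the tables already held those events. Onset is therefore the natural reading. The alternative, that any event still ongoing at first dose counts, would also depart from the protocol, because it would bring in pre-dose events that stayed the same or improved.

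**2. What does each rule do with each kind of event?**

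| Event | Protocol 11.10 | SAP 6.1 |
|---|---|---|
| Starts on drug | Counted | Counted |
| Starts in screening, unchanged on drug | Not counted | Not counted |
| Starts in screening, worsens on drug, one record with pre-dose onset | Counted | Not counted |
| Starts in screening, worsens on drug, new record dated at the worsening | Counted | Counted |

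The rules disagree only in the third row.

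**3. Can the third row occur?** Collection from consent and a screening phase of about 90 days make pre-dose events possible by design. Whether a worsening stays on the existing record depends on an eCRF convention that neither document gives.

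**4. Which outputs are touched?** The SAP 6.1 tables built on the flag include overall incidence, severity, and the clusters for sleep, depression and anxiety. Amyloid status is disclosed during screening (Protocol 9.1.2). Anxiety that began after disclosure and worsened on drug, kept on one record, would be missing from the anxiety cluster and the severity table. The scale summaries in SAP 6.4.1 describe scores and do not replace event incidence. A screening-onset event that worsened and led to drug withdrawal could also appear in the SAP's listing but not in the matching table.

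**5. How large is it?** The SAP gives 557 randomized subjects. It does not give the number of events ongoing at first dose or the rule for recording a change in severity. The loss therefore runs from zero (every worsening gets a new record) to all events in the third row (none does), and the documents do not narrow it.

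**The case against.** The strongest reply is that the protocol already treats a worsening as an event. Its definition in 12.1.1 covers "any occurrence that is new in onset or aggravated in severity or frequency from the baseline condition". Sections 9.9.4 and 9.9.6 require clinically relevant changes in examinations and laboratory results to be entered in the AE section of the eCRF. If a worsening is entered as its own event, dated when it happened, the SAP window captures it. This stands, and it is why the loss may be zero. It does not settle the matter, because none of these sections says that an event already on the eCRF gets a new record and onset date when it worsens. If that always happened, the second part of the protocol's definition would be largely redundant.

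A reader might also infer that the SAP hides worsening of liver enzymes, the reason dosing was stopped. The documents do not support that. The laboratory section of the SAP and 6.1.1 give changes from baseline, counts above 5 and 8 times ULN, combined transaminase and bilirubin or INR criteria, Kaplan-Meier curves and an eDISH plot. The on-treatment criteria do not require a normal baseline, and Attachment 6 flags ALT or AST above 3 times ULN. Shift tables alone would miss an already high value that rises further, but the other outputs largely cover it. Meeting the liver discontinuation criteria is also reportable as an SAE (Protocol 10.2 and Attachment 3).

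Two further points limit the effect. The listings of deaths, SAEs and events leading to discontinuation or termination keep screening-onset events visible, although not as incidence. A subject with another treatment-emergent event still counts in the overall row, and only the term that worsened is affected.

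Finally, Protocol section 11 leaves details to the SAP, and the summaries are descriptive, so no test or decision rule changes. That lowers the priority. It does not justify dropping part of a stated definition without saying so.

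**Conclusion.** The mismatch holds. SAP 6.1 omits the protocol's worsening part, and applied as written it excludes a screening-onset event that worsens on drug and stays on one record.

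It is tempting to go further and say that on-drug worsening is lost from the safety tables. The documents do not establish that: the loss depends on an unstated recording convention and may be zero. They also give no basis for a number of subjects affected. The exposure lies mainly in non-laboratory events.

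The conclusion assumes that the SAP window is applied by onset date, as its neighbouring rules indicate. This is a low-priority correction, worth making because it is cheap and aligns the tables with the protocol.

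**What to change.** In SAP 6.1, replace the definition with wording such as: *An AE is treatment-emergent if its onset falls between first dose and 7 days after last dose, or if it began before first dose and its intensity increased in that period; in the second case it is dated at the increase.* Apply the same worsening rule to the off-treatment period, taking the intensity at the end of the on-treatment window as the reference.

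If the eCRF requires a new record at each increase in severity, state that in SAP 6.1 instead, because the date rule then already covers these events. If the narrower definition is intended, record it as a departure from Protocol 11.10 with a reason.

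The cost is one clause and one program condition. The condition needs the severity at first dose and the date of any later increase. The documents do not describe how the eCRF stores severity, so check that first.

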### 10.2. Discontinuation of Study Treatment

If a subject's study treatment must be discontinued before the end of the treatment regimen, this will not result in automatic withdrawal of the subject from the study.

Subjects who discontinue study treatment prematurely will be asked to complete all regular study visits through the end of the study. To reduce burden on subjects and increase compliance, the focus will be on collecting primary and secondary clinical outcome measures and reducing other assessments in these subjects.

Subjects who meet the criteria for discontinuation of study treatment should have the event reported as an SAE and should follow the SAE reporting as outlined in Section 12.3.2.

A subject's study treatment will be discontinued if the investigator believes that for safety reasons (eg, AE) it is in the best interest of the subject.

For subjects during the first 3 months of treatment with study drug, treatment must be discontinued if any of the following occurs (for details see Attachment 3):

- ALT or AST  $>5 \times \text{ULN}$
- ALT or AST  $>3 \times \text{ULN}$  and total bilirubin  $>2 \times \text{ULN}$  or International Normalized Ratio (INR)  $>1.5$
- ALT or AST  $>3 \times \text{ULN}$  with the appearance of fatigue, nausea, vomiting, right upper quadrant pain or tenderness, fever, rash, and/or eosinophilia  $>5\%$

For subjects that have completed 3 months of treatment with study drug, treatment must be discontinued if any of the following occurs (for details see Attachment 3):

- ALT or AST  $>8 \times \text{ULN}$
- ALT or AST  $>5 \times \text{ULN}$  for more than 2 weeks
- ALT or AST  $>3 \times \text{ULN}$  and (total bilirubin  $>2 \times \text{ULN}$  or INR  $>1.5$ )
- ALT or AST  $>3 \times \text{ULN}$  with the appearance of fatigue, nausea, vomiting, right upper quadrant pain or tenderness, fever, rash, and/or eosinophilia ( $>5\%$ )

Note: Abnormal liver enzymes greater than  $3 \times \text{ULN}$  at any time during the treatment phase should be confirmed within 24-72 hours (See Attachment 3).

If the subject has a QTcF interval of >500 msec and/or QTcF increase versus baseline of >60 msec, confirmed upon repeat ECG, after consultation with the sponsor's medical monitor, treatment must be discontinued.

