1. INTRODUCTION

This statistical analysis plan (SAP) contains definitions of analysis populations, derived variables and statistical methods for the analysis of efficacy and safety for study 54861911ALZ2003.

Screening, randomization, and dosing in this study was stopped on 17 May 2018. Randomized subjects were to continue in the double-blind treatment phase without treatment (as allowed by protocol) for approximately 3 to 6 months from cessation of dosing. This permitted continued safety monitoring of the subjects per protocol. The planned last-patient-out date is 17 September 2018, except for some subjects who may require further follow-up.

At the time of cessation of screening and randomization, 557 (34%) subjects of the planned 1650 had been randomized. The planned duration of treatment was 54 months. As of the time of cessation of dosing, no subject had more than 27 months of treatment and 447 had 12 months of treatment or less.

As a result of the significantly reduced sample size, the objectives of the study as stated in the protocol and in Section 1.1 below cannot be evaluated. Safety outcomes will be summarized with descriptive statistics. The planned interim analysis of CSF A β ₁₋₄₀ was performed but other planned interim analyses will not be performed. Between-group comparisons of selected efficacy outcomes will be performed. Other efficacy outcomes will be summarized with descriptive statistics

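### The SAP's rule for adverse events with incomplete dates has no exit at the end of the treatment-emergent window, so an event shown by its partial date to have begun off drug meets both the on-treatment and the off-treatment definition

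*SAP*

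**What the plan says.** Three sentences in SAP section 6.1 Adverse Events bear on this.

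- **Fully dated events.** "Any AE occurring on or after the date of the initial administration of study medication through the day of last dose plus 7 days is" classed as treatment-emergent.
- **Partial or missing dates.** For these, "then the event will be considered to be treatment emergent unless it is known to be prior to the first administration of study medication". That exception is to be judged "based on a partial onset date or resolution date". It is the only exception given.
- **Off-treatment events.** "AEs in the off-treatment period are the AEs with onset more than 7 days after the last dosing". This sentence does not say how a partial date is handled.

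The opening of section 6 makes the split matter: "All safety summaries will be presented for the on-treatment period and the off-treatment period". The only other rule for incomplete dates, SAP Attachment 5, covers concomitant medications.

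Off-drug observation was planned. The SAP introduction states "Screening, randomization, and dosing in this study was stopped on 17 May 2018" and "Randomized subjects were to continue in the double-blind treatment phase without treatment (as allowed by protocol) for approximately 3 to 6 months". It gives 17 September 2018 as the planned last-patient-out date, with longer follow-up for some subjects. Protocol section 10.2 adds, for those who had stopped earlier, "Subjects who discontinue study treatment prematurely will be asked to complete all regular study visits through the end of the study". Protocol section 12.3.1 has adverse events collected up to the last study-related procedure, so off-drug events do reach the database.

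**The concern.** Treating an event of unknown timing as treatment-emergent is a sound, cautious default. Here the default also covers events whose timing is known well enough to place them outside the window. A recorded month that lies wholly before the first dose takes an event out of the treatment-emergent set. A recorded month that lies wholly beyond the window does not.

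The result depends on whether the day was recorded. An event dated 10 July 2018 in a subject last dosed on 17 May is off-treatment only. The same event recorded as JUL 2018 is treatment-emergent under one sentence and off-treatment under another, and two programmers could reasonably build different tables from the same data.

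At stake is the separation of on-treatment from off-treatment adverse events. The SAP introduction says that the trial's objectives can no longer be evaluated and that safety will be summarised descriptively, so these tables are a central part of what the stopped trial reports.

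**Working it through.** There is no planned figure to reproduce. The check applies the sentences as written to month-only onset dates.

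**Inputs.** Dosing stopped on 17 May 2018 and the planned last-patient-out date is 17 September 2018 (SAP section 1). The window ends at last dose + 7 days (SAP section 6.1 Adverse Events).

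**Window.** For a last dose on 17 May 2018 it ends on 17 + 7 = 24 May 2018.

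**Classification.** An onset is certainly off-treatment when the first day of the recorded month is later than 24 May.

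| Recorded onset | Earliest possible day | Days after last dose | Partial-date sentence | Off-treatment sentence |
|---|---|---|---|---|
| MAY 2018 | 1 May | cannot be settled | treatment-emergent | not established |
| JUN 2018 | 1 June | 14 + 1 = 15 | treatment-emergent | met |
| JUL 2018 | 1 July | 15 + 30 = 45 | treatment-emergent | met |
| AUG 2018 | 1 August | 45 + 31 = 76 | treatment-emergent | met |
| SEP 2018 | 1 September | 76 + 31 = 107 | treatment-emergent | met |

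Four of the five months meet both definitions. At the lower boundary the rule works: with an assumed first dose on 1 September 2017, an onset of AUG 2017 is correctly left out of the treatment-emergent set.

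**Earlier discontinuers.** With an assumed last dose on 1 December 2017 the window ends on 8 December 2017. Month-only onsets of January, May, June, July, August and September 2018 were tested, and all six meet both definitions.

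**Calendar time exposed to the conflict, last dose 17 May 2018.**
- To the planned last-patient-out date: 14 + 30 + 31 + 31 + 17 = 123 days, of which 123 − 7 = 116 lie beyond the window.
- The 7 days from 25 to 31 May would be recorded as MAY 2018, which is ambiguous. That leaves 116 − 7 = 109 days (1 June to 17 September) in which a month-only date settles the matter.
- If a subject left after 3 months, on 17 August: 14 + 30 + 31 + 17 = 92 days, then 92 − 7 = 85 beyond the window and 85 − 7 = 78 resolvable.

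**After the correction.** With an exit at the upper boundary, JUN to SEP 2018 become off-treatment only. MAY 2018 and completely missing dates stay treatment-emergent.

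**The case against.** The strongest reply is that the paragraph already contains the answer. Its closing sentence is not limited to complete dates, and JUL 2018 after a last dose on 17 May is plainly more than a week later. A reader might infer from the partial-date sentence alone that such events will definitely be tabulated as on-drug. The documents do not support that, because both sentences apply. What stands is a conflict that the SAP does not resolve.

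A second reply is that Protocol section 11.10 defines treatment-emergent events by onset in the double-blind phase, and Protocol section 1.1 keeps subjects in that phase after dosing stopped. Counting these events as treatment-emergent would then agree with the protocol. But the SAP replaces that definition with a cut at last dose + 7 days and applies it to fully dated events. The phase-based definition cannot explain why only incompletely dated events should escape the cut.

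A third reply concerns consequence, and most of it stands. The liver-enzyme tables, time-to-event curves and eDISH plot in SAP section 6.1.1 use laboratory values, so this rule does not touch them. Serious events and events of special interest must be reported within 24 hours of site awareness, which makes vague dates less likely. Tables count subjects with at least one occurrence, so a single misplaced event need not change any cell. The safety analysis is descriptive.

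A reader might also infer a bias between arms, since the liver stopping rules in Protocol section 10.2 could give the active arms more early stoppers and so more off-drug time. The documents report neither discontinuation nor off-drug follow-up by arm, so this is conjecture. If such an imbalance existed, it would add events to the active arms' on-treatment tables rather than hide them.

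**Conclusion.** The point holds as a defect in a stated rule. Followed literally, SAP section 6.1 puts an adverse event whose partial onset date proves it began after the window into both periods, or leaves its place to the programmer. This follows from the wording and needs no numerical assumption.

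Its size cannot be computed. The documents give no count of partially dated events, no adverse event rate and no number of subjects on drug at cessation. A reader might be tempted to multiply follow-up time by an assumed event rate and an assumed share of partial dates. Any such total would rest on unsourced rates. Using all 557 randomised subjects would treat everyone as still on drug on 17 May 2018, and using 116 days would include a week that a month-only date cannot resolve. The supportable statement is that, for a subject dosed until 17 May 2018 and followed to the planned end, up to 109 days of observation are exposed to the conflict (78 for a 3-month exit), and that the number of events may be small. No difference between arms is shown. Severity: minor.

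**What to change.** Extend the exception in the partial-date sentence of SAP section 6.1 Adverse Events with a clause such as: *or the partial onset date shows that the event began later than last dose + 7 days, in which case it is an off-treatment event*. Only the onset date can serve here, because a late resolution date does not show a late start. Add that each adverse event is assigned to one period only.

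The cautious default is kept where it belongs: partial dates compatible with the window, and completely missing dates, remain treatment-emergent.

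The cost is one clause, one short sentence and one extra condition in the program that sets the treatment-emergent flag. No new data are needed.
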